6 ENDPOINTS

EFFICACY/EFFECTIVENESS ENDPOINTS

The clinical endpoints listed below will be assessed by line of therapy (LOT) (1st line, \geq 2nd line) in the ABC/MBC setting and reported.

- Real-World Tumor Response (rwTR)
- Real-World Progression-Free Survival (rwPFS)
- Overall Survival (OS)

Although a comparison of treatment regimens is not the primary intent of this NI study design, some clinical endpoints of interest may be separately summarized by different treatment regimens.

SAFETY ENDPOINTS

Safety will be assessed by adverse events (AEs), adverse events of special interest (AESIs), SAEs, and results of standard laboratory tests.

PHYSICIAN-REPORTED ENDPOINTS

Physician responses to quality of life questionnaires – ECOG performance status and G8 Screening Tool – will be evaluated at baseline and post-baseline.

ECOG Performance Status

ECOG performance status is a 6-level item ranging from “0: Fully active, able to carry on all pre-disease performance without restriction” to “5: Dead.” Physicians complete this assessment for patients at baseline and at every post-baseline standard of care visit.

G8 Screening Tool

The G8 Screening Tool consists of 7 items based on the Mini-Nutritional Assessment and a single item covering the patient’s age. Specifically, the G8 assesses food intake, weight changes, mobility, neuropsychological problems, body mass index, prescription count, and health status compared to similarly aged patients. Points are associated to each item and index score is calculated by summing points. The index score ranges in value from 0-17. If any of the 8 items is missing, the total score is missing. See Appendix 1 Data Derivation Details for item point values.

Physicians complete the G8 at baseline (prior to starting palbociclib) for patients \geq 70 years of age, and then for these same patients and then at 1 month, 2 months, 3 months, 6 months, 9 months, 12 months, etc. (i.e., every three months until the end of treatment with palbociclib) post-baseline. Additional timepoints will be added based on sample size.

PATIENT-REPORTED ENDPOINTS

Patient responses to quality of life questionnaires – EORTC QLQ-C30 and ADL – will be evaluated at baseline and post-baseline.

EORTC QLQ-C30

The EORTC QLQ-30 is a 30-item questionnaire composed of 5 multi-item functional subscales (physical, role, cognitive emotional, and social functioning), 3 multi-item symptom scales (fatigue, nausea/vomiting, and pain), a global health/quality of life (QoL) subscale, and 6 single items assessing other cancer-related symptoms (dyspnea, sleep disturbance, appetite, diarrhea, constipation, and the financial impact of cancer). For functional and global QoL scales, higher scores represent a better level of functioning and are converted to a 0 to 100 scale. For symptom-oriented scales, a higher score represents more severe symptoms. Missing data will be imputed according to the EORTC guidelines, and questionnaires will be considered as missing if >50% of the items were missing.. See scoring algorithm in Appendix 1 Data Derivation Details.

Patients (regardless of age) complete the EORTC QLQ-C30 at baseline (prior to starting palbociclib) and then at 1 month, 2 months, 3 months, 6 months, 9 months, 12 months, etc. (i.e., every three months until the end of treatment with palbociclib) post-baseline.

Activities of Daily Living

The Activities of Daily Living (ADL) is a subscale of the Medical Outcomes Study (MOS) Physical Health. It is applicable to patients ≥ 70 years of age. The MOS Physical Health Scale measures a broad range of physical functioning that include bathing, dressing, toileting, transfer, continence, and feeding activities. Items for each of the six activities are rated on a 3-point Likert scale measuring independence in performing the activity (i.e., no assistance needed, partial assistance needed, unable to do without assistance). No imputation will be performed for missing items.

Katz Index¹⁷ will be used to present items in a hierarchy of severity or difficulty of performing each task and a total score will be summarized for the six items. Independence is defined as performing these tasks without supervision, guidance or personal assistance while dependence is defined as doing the tasks with supervision, guidance or personal assistance. See Appendix 1 Derived Data Details for scoring details.

Patients ≥ 70 years of age complete the ADL at baseline (prior to starting palbociclib), and then at 1 month, 2 months, 3 months, 6 months, 9 months, 12 months, and so on (i.e., every three months until the end of treatment with palbociclib) post-baseline.

7 HANDLING OF MISSING VALUES

Given the prospective observational multi-site study design, missing data may occur, even though effort will be made to ensure consistent and complete data are collected. All available patient data will be used for analysis.

Date Imputations

For initial diagnosis date, date of prior therapy, date of prior radiation, or date of prior surgery:

- If the date of initial diagnosis has nonmissing month and year but the day is missing, the 15th will be inserted as the day.
- If the date of initial diagnosis has nonmissing year but the month and the day are missing, June 30th will be inserted.

For all other dates:

- If the variable is a stop or end date and day of the month is missing, the last day of the month will be imputed. All other dates with missing day of the month will be assigned the first day of the month.
- If the variables is a stop or end date and day and month are missing, 31 December will be imputed. All other dates with missing day and month will be assigned to 1 January.

Dates missing the year will be treated as completely missing.

Questionnaire Imputations

Missing data patterns will be explored using multivariable regression cross sectional analysis conducted at baseline and selected 6-month time points with completion of instrument (EORTC QLQ-30, G8, or ADL) coded as '1' and non-completion of the same instrument coded as '0'.

Additional information on missingness (e.g. reasons for withdrawal) may be explored. Scores associated with the EORTC QLQ-C30, G8, and ADL are addressed in section 8.9 Analyses Quality of Life Endpoints and Appendix 1 Data Derivation Details.

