8 STATISTICAL ANALYSIS

This study has a convenience sample; thus, results may not be generalizable to the entire population with the disease. Due to the study's exploratory nature, study measures will be summarized descriptively. Furthermore, any p value reporting should be placed in a descriptive framework for hypothesis generation and any such inferential analysis is intended to guide further research.

All analyses will be conducted using SAS® version 9.4 or higher.

The intention is to analyze all available data. In the advent that COVID may cause gaps in subject data or require adjustments to statistical methodologies, our intent is to address such issues if or as needed. Both ICON and Pfizer have internal guidances and recommendations on file to assist with decision-making with regards to COVID-related data issues and these will be consulted if or as needed.

GENERAL METHODS

For continuous variables, means, standard deviations (SD), medians, minimums, maximums, and missing will be reported. For discrete variables, frequencies and percentages will be reported. Missing or unknown categories for each variable also will be presented. Percentages will be calculated excluding missing or unknown values. 95% Confidence Intervals (CI) are two-sided.

All summaries will be performed for all patients in the corresponding analysis set and by treatment combination defined at study entry within the corresponding analysis set:

- Palbociclib + Letrozole or Anastrozole
- Palbociclib + Fulvestrant
- Palbociclib + Exemestane
- Other

The baseline record is defined as the last observed measurement prior to palbociclib administration. Change from baseline is defined as the post-baseline value minus the baseline value.

Time in days between two dates will be calculated using the formula most recent date minus earlier date plus 1. For time in months, the same formula for days will be applied but then divided by 30.4. For time in years, the same formula for days will be applied but then divided by 365.25.

Variable definitions are found in Appendix 1 Data Derivation Details.

DISPOSITION OF SUBJECTS

A subject disposition summary will be reported. Subjects' study completion date and reason for premature termination will be reported in listing format. Number of subjects with initial diagnosis and with recurrent diagnosis will be reported in table and listing format.

DEMOGRAPHIC AND BASELINE CLINICAL CHARACTERISTICS

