APPENDIX 1: DERIVED DATA DETAILS

Study End Date: the earliest of study withdrawal date or last contact visit date

Study Duration: defined in days as study end date minus baseline date +1.

Study Day: post-baseline visit or event date minus baseline date +1. For pre-baseline visits or events, study day is defined as pre-baseline visit or event date minus baseline date. Note there is no study equal to 0.

Age at baseline: defined in years as baseline date minus date of birth +1 divided by 365.25.

Duration of disease: defined in days from initial diagnosis date to study enrollment date.

Duration of ABC/MBC disease: defined in days from ABC/MBC diagnosis date to study enrollment date.

Disease-free interval: time from the end of adjuvant/neoadjuvant treatment to the first disease recurrence.

Paloma-3 disease-free interval: defined in days as the time between first diagnosis of breast cancer and onset of metastatic disease or disease recurrence.

Treatment-free interval: defined in days as the time from last dose of prior chemotherapy to first MBC therapy or first study dose whichever occurred earlier.

Line of Therapy (LOT):

Clinical outcome endpoints will be summarized by LOT which is defined based on the number of therapies taken after initial diagnoses of ABC or MBC, but before palbociclib treatment start:

- 1st line: patients had no LOT in the ABC/MBC setting before palbociclib initiation
- 2nd line: patients had one LOT in the ABC/MBC setting before palbociclib initiation
- 2⁺ line: patients had >1 LOT in the ABC/MBC setting before palbociclib initiation

Best Tumor Response: best overall tumor response recorded from palbociclib treatment start until first documentation of progressive disease. Only response assessments recorded on or before the start date of next subsequent line of treatment will be considered.

Clinical Benefit: a best overall tumor response of complete response or partial response at any time, or stable disease for at least 24 weeks post-study treatment initiation. Only response assessments recorded on or before the start date of next subsequent line of treatment will be considered.

Overall Survival (OS): is defined as time (months) from initiation of the palbociclib combination treatment to date of death, due to any cause.

First Hormonal Therapy After Stage III or IV Diagnosis: the first recorded MBC or adjuvant hormonal therapy after initial diagnosis of stage IIIb or IV MBC or ABC.

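### Partial initial-diagnosis and ABC/MBC-diagnosis dates are imputed by different rules with no order check, so a de novo patient missing the same date parts is dated metastatic before the cancer

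*SAP*

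**What the plan says.** SAP section 7, Date Imputations, has two sets of rules. The first is introduced by "For initial diagnosis date, date of prior therapy, date of prior radiation, or date of prior surgery". For a missing day it says "If the date of initial diagnosis has nonmissing month and year but the day is missing, the 15th will be inserted as the day". For a missing day and month it says "If the date of initial diagnosis has nonmissing year but the month and the day are missing, June 30th will be inserted". The lead-in lists four kinds of date, but both bullets name only the initial diagnosis.

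The second set covers everything else. Stop and end dates go to the end of the month or year. For the rest, "All other dates with missing day of the month will be assigned the first day of the month" and "All other dates with missing day and month will be assigned to 1 January". The ABC/MBC diagnosis date is not in the first list and is not a stop date, so it falls here.

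Appendix 1 treats the two diagnosis dates as separate variables. Duration of disease starts at initial diagnosis, and a second measure reads "Duration of ABC/MBC disease: defined in days from ABC/MBC diagnosis date to study enrollment date". The PALOMA-3 disease-free interval runs from first breast cancer diagnosis to metastatic onset or recurrence. Section 8, General Methods, computes a time in days as "most recent date minus earlier date plus 1". Line of therapy (LOT) is the number of therapies taken after ABC/MBC diagnosis "but before palbociclib treatment start". Neither document sets an order check or a cap on an imputed date.

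**The concern.** For a de novo patient, initial diagnosis and ABC/MBC diagnosis are one event. These patients are in scope, since section 5 lists de novo versus recurrent as a potential subgroup. The two rules pull that single event apart, and in the impossible direction: the initial diagnosis goes to the middle of the period and the metastatic diagnosis to its start.

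At stake are derived baseline measures. Section 8 summarises the PALOMA-3 interval and the duration of ABC/MBC disease as disease characteristics, and in a descriptive study such tables are part of the result.

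A related gap concerns treatment history. If prior therapy, radiation and surgery also go to the 15th or 30 June, nothing stops an imputed prior date from landing on or after the first palbociclib dose. The treatment-free interval and the months from last prior radiation to first study dose both use such dates.

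**Working it through.** The plan states no figure to reproduce, so the check applies its rules to dates.

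**Inputs.** Imputation rules: SAP section 7. Interval definitions: SAP Appendix 1. Interval formula: SAP section 8, General Methods. Let I be the imputed initial-diagnosis date, M the imputed ABC/MBC-diagnosis date and E enrolment. I take I and M as the end points of the PALOMA-3 interval for a de novo patient.

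**Step 1. De novo, both dates lacking the same parts.** The true difference is 0.

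| Known | I | M | M − I |
|---|---|---|---|
| Month and year | 15th | 1st | −14 days |
| Year only | 30 June | 1 January | −180 days (−181 in a leap year) |

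The second row follows because 30 June is day 31 + 28 + 31 + 30 + 31 + 30 = 181 of the year, and 181 − 1 = 180.

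**Step 2. Durations.** ABC/MBC duration minus disease duration = (E − M) − (E − I) = I − M = 14 or 180/181 days. Adding 1 to both durations cancels. A part therefore lasts longer than the whole, whatever the enrolment date.

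**Step 3. PALOMA-3 interval.** Equal dates give 0 + 1 = 1 day.

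- Later minus earlier plus 1: 14 + 1 = 15 days, or 180 + 1 = 181 days (182 in a leap year). 181/30.4 = 5.95 months and 182/30.4 = 5.99 months.
- Signed, M − I + 1: −13 days, or −179 days (−180 in a leap year). These are visibly wrong.

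**Step 4. De novo, only one date partial.** Assume true dates uniform over a 365-day year. The share with M before I is:

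- initial diagnosis lacks the day, ABC/MBC complete: 12 × 14/365 = 46%;
- initial diagnosis year only, ABC/MBC complete: 180/365 = 49%;
- initial diagnosis complete, ABC/MBC year only: 364/365 = 99.7%.

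**Step 5. Prior-therapy dates, if the mid-point bullets cover them.** Take a year-only prior therapy in the calendar year of palbociclib start. It is dated 30 June. With a start on 1 March 2017 it falls 30 + 30 + 31 + 30 = 121 days after the start. The share dated on or after the start depends on the assumed distribution:

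- Year only, starts uniform over the year: 181/365 = 49.6%.
- Year only, both dates uniform with therapy truly before start: (181 × 180/2)/(365 × 364/2) = 16,290/66,430 = 24.5%.
- Day missing, same month as start, starts uniform: 12 × 15/365 = 49.3%.
- Day missing, same month, therapy truly before start: 12 × (15 × 14/2) = 1,260 of 7 × 465 + 4 × 435 + 378 = 5,373 pairs, or 23.5%.

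The ranges are about 25–50% (year only) and 23–49% (day missing), and only among records sharing the year or month of palbociclib start.

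**Step 6. After the fix.** With one rule for both diagnosis dates, the Step 1 gap is 0 days. With imputed prior dates held before palbociclib start, Step 5 produces no violations.

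**The case against.** The strongest counter-case is that the effect is confined to baseline intervals in an unknown number of records.

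- **Line of therapy.** A reader might infer that imputation moves pretreated patients into 1st line and so contaminates rwTR, rwPFS and OS, which are reported by LOT. The documents do not support that. The mid-point rule applies to records already identified as prior therapy. Breast cancer treatment is collected by setting and by timing relative to palbociclib (Table 1, footnote 3, in both documents), and the SAP nowhere says that LOT is computed from imputed dates. This part of the objection stands.
- **De novo label.** A reader might infer that the de novo/recurrent classification is corrupted. Section 5 lists it as a status at enrolment, and no derivation from dates is given. This also stands.
- **Hidden sign.** The formula in General Methods may be ordinary end-minus-start wording and not an instruction to reorder inverted dates. That is a fair reading, so the spurious positive interval is conditional. Read the other way, the interval is negative, which is equally unusable.
- **Scope of the bullets.** Both name only the initial diagnosis, so extending them to therapy, radiation and surgery rests on the lead-in. True; but otherwise those three listed dates have no explicit rule.
- **Frequency.** Protocol 8.6 provides for querying missing data, and the eCRF may hold a single date for de novo disease. Either could shrink the effect. But data come from existing charts (protocol 8.4.1), a query cannot recover what a chart lacks, and Appendix 1 names two dates.

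**Conclusion.** The inconsistency between the two diagnosis-date rules is real. When a de novo patient's two dates lack the same parts, the stated rules always give an impossible order: metastatic disease 14 days (day missing) or 180/181 days (year only) before the initial diagnosis. ABC/MBC duration exceeds disease duration by the same amount. The PALOMA-3 interval is 15 or 181/182 days instead of 1 if taken as later minus earlier plus 1. This assumes that the two dates are recorded and imputed separately, as Appendix 1 implies.

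The prior-treatment part is conditional on the mid-point bullets covering those dates. It then distorts the treatment-free interval and the months from last radiation to first dose. The shares of 25–50% and 23–49% reflect assumed date distributions; a flat figure of about half would be the upper end only.

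Misclassified line of therapy, and any effect on the outcomes reported by line, would follow only if LOT were derived from imputed dates. No formal hypothesis test is planned (protocol 8.7), so none is at risk. The total number of affected patients cannot be estimated, because the documents do not give the share of partial dates.

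**What to change.** In SAP section 7 and Appendix 1:

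1. Use the same imputation rule for initial and ABC/MBC diagnosis dates.
2. Where disease is recorded as de novo, set the two dates equal, using the more complete one.
3. Constrain imputed dates so that initial diagnosis ≤ ABC/MBC diagnosis ≤ palbociclib start.
4. Require records identified as prior therapy, radiation or surgery to fall before palbociclib start.
5. Reword the mid-point bullets to cover all four dates in their lead-in.
6. State that recorded prior status and treatment setting take precedence over imputed dates when LOT is assigned.
7. Flag negative intervals for review instead of reordering the dates.

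The cost is a few lines of SAP text and derivation code, with no new data collection.

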Overall palbociclib treatment will be summarized as below for the FAS overall and by LOT:

- Number of cycles of palbociclib received
- Length of palbociclib treatment (months)
- Treatment disposition: (still receive palbociclib, discontinued palbociclib)

Palbociclib prescribing and treatment patterns will also be explored by cycle. For each cycle, below will be summarized:

- Starting dose (if less than 125mg, present reason)
- Primary reason for selecting palbociclib for the first cycle
- Dose modification (type, dose received after modification, reason)

Treatment patterns following enrollment will be reported, which include only lines started at enrollment:

- Type of therapy received (such as chemotherapy, hormonal therapy, other therapy)
- Agent (drug) composition of the treatment regimen received
- Time from initiation of treatment to initiation of each subsequent lines of treatment

- Time from discontinuation of previous line to initiation of the subsequent line of treatment
- Time from the start to end of each treatment line (in months for the total duration). This measure will be presented overall and by the top four regimens received in the line.

The sequence of agents/combination regimens received for first-line treatment in the ABC/MBC setting and subsequent lines of treatment will be presented. The proportion of all patients with each unique sequencing pattern will be reported for the overall study sample. Type of therapy sequencing (e.g., endocrine only, chemotherapy only, endocrine therapy combined with target therapy) will also be presented in the same format.

CLINICAL OUTCOMES

rwTR, rwPFS, and OS will be assessed by LOT (1st line, \geq 2nd line) in the ABC/MBC setting for the FAS. Based on the nonrandomized, observational nature of the study design, no clinical endpoints will be separately assessed and compared between specific treatment regimens.

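### Partial on-study stop dates are imputed to the latest possible day and partial start dates to the earliest, with no bound, so affected line durations can only be lengthened and an imputed stop can fall after death, last contact or the next line's start

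*SAP*

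**What the plan says.** SAP Section 7 (Date Imputations) has two sets of rules.

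- The first set is introduced by "For initial diagnosis date, date of prior therapy, date of prior radiation, or date of prior surgery" and uses mid-points: the 15th, or 30 June if the month is also missing. Its bullets name only initial diagnosis, but the heading includes prior treatment.
- The second set covers every other date. The rule for a stop reads: "If the variable is a stop or end date and day of the month is missing, the last day of the month will be imputed"; and "If the variables is a stop or end date and day and month are missing, 31 December will be imputed". The rest: "All other dates with missing day of the month will be assigned the first day of the month"; and "All other dates with missing day and month will be assigned to 1 January". A partial start date or death date falls in this last group.

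Neither Section 7, Section 8 nor Appendix 1 limits an imputed date by another known date. Appendix 1 defines a study end date but does not use it as a limit.

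These dates feed the Study Drug Exposure outputs in SAP Section 8: length of palbociclib treatment, "Time from the start to end of each treatment line (in months for the total duration"), and "Time from discontinuation of previous line to initiation of the subsequent line of treatment". Section 8, General Methods, gives the interval rule: "Time in days between two dates will be calculated using the formula most recent date minus earlier date plus 1". Appendix 1 divides line duration by 30.4 to give months. It derives the gap between lines from the previous line's initiation, although the variable is named from discontinuation.

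**The concern.** The two imputation directions work together. A partial start moves back and a partial stop moves forward, so any line with a partial date is measured as its true length or longer. Because the error is never negative, it does not average out across patients.

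The missing bound also allows impossible sequences. If a patient stops treatment and dies in the same month with both days missing, death is set to the first of that month and treatment ends on its last day. If the stop and the next line's start are both known only to the same month, the lines overlap by construction. With several interim analyses planned (SAP Section 4), a year-only stop can be set to a 31 December that lies beyond the data cut.

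Protocol Section 8.1 makes prescribing and treatment patterns the primary goal, and treatment sequence is a stated objective. Length of treatment and line duration are direct outputs for both.

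**Working it through.** The documents state no figure on this point, so there is nothing to reproduce. The check applies the Section 7 rules to every calendar day of 2017–2020 (1,461 days), assuming true dates are uniform over the calendar.

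**1. Mean error per partial date**

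| Partial date | Imputed to | Mean shift (days) | Maximum |
|---|---|---|---|
| Stop, day missing | month end | 14.7 later | 30 |
| Start, day missing | 1st | 14.7 earlier | 30 |
| Stop, month and day missing | 31 December | 182.1 later | 365 |
| Start, month and day missing | 1 January | 182.1 earlier | 365 |

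With both days missing, the duration excess is 2 × 14.73 = 29.5 days, or 29.5 / 30.4 = 0.97 month.

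**2. Worked example.** The true line runs 20 March to 5 September 2018 and the next line starts on 12 September. Duration = stop − start + 1.

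- True: 170 days; 170 / 30.4 = 5.59 months.
- Stop day missing: stop becomes 30 September; 195 days = 6.41 months; 19 days (12 to 30 September) overlap the next line.
- Both days missing: 1 March to 30 September; 214 days = 7.04 months.
- Year-only stop: 31 December; 287 days = 9.44 months; 111 days overlap.
- Stop capped at the day before the next line (11 September): 176 days = 5.79 months and no overlap, whether the day or the month is missing.

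**3. How often the imputed stop reaches the next line's start**, by true gap, with a complete next start date:

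| True gap (days) | Stop day missing | Year-only stop |
|---|---|---|
| 7 | 77% | 98% |
| 14 | 54% | 96% |
| 28 | 8% | 92% |
| 90 | 0% | 75% |
| 180 | 0% | 51% |

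These are shares of records with a partial stop, not of all records.

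**4. Effect on the overall mean duration.** Excess = share of partial records × mean shift / 30.4. The share is unknown; I assume 2% to 30%.

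- Stop day missing: 0.02 × 14.73 / 30.4 = 0.01 month, up to 0.30 × 14.73 / 30.4 = 0.15 month.
- Both days missing: 0.02 to 0.29 month. At 10% this is 0.10 × 29.5 = about 3 days.
- Stop month missing: 0.02 × 182 / 30.4 = 0.12 month, up to 1.80 months.

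**5. What the cap achieves.** With a day-missing stop, capping at the day before the next line cuts the mean stop error from 14.7 to 5.3 days for a true gap of 7 days and to 10.0 days for 14. For 28 days it stays at 14.6. The cap removes overlap with a known next start; it reduces the upward bias but does not remove it.

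**6. The gap between lines.** In the worked example the true value is 12 September − 5 September + 1 = 8 days. With the stop day missing, the unsigned General Methods formula gives 30 September − 12 September + 1 = 19 days, so an overlap appears as a gap. The Appendix 1 derivation gives 12 September − 20 March + 1 = 177 days and does not use the stop date at all.

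**The case against.** **Only partial dates are affected, and there may be few.** Protocol Sections 8.4.1, 8.6 and 8.8 provide for entry after each standard-of-care visit, queries for missing or unclear data, and remote review of critical variables. This stands as a limit on size. It does not exclude partial dates, and Section 7 provides for them.

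**Reach is limited.** rwPFS and OS run from palbociclib initiation to progression or death and do not use line stop dates. The affected outputs are descriptive and no formal hypothesis testing is planned. This stands too.

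**A reader might infer that adjacent lines will generally overlap.** They overlap only when the stop is partial and the next line starts within the imputed month or year. With a day-missing stop and a true gap of 45 days or more, overlap is nil.

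**A reader might infer that gaps between lines are also biased one way.** They are not. Under the unsigned formula with the stop day missing, a true 7-day gap is overstated in 51% of cases and understated in 43% (mean +2.6 days), while a true 28-day gap is understated by 14.6 days on average. Moreover, the variable-specific derivation in Appendix 1 leaves the stop date out, so an imputed stop does not alter the gap as it is now written. That derivation is a separate drafting error.

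**A reader might want the mid-point rule extended to on-study dates.** Its mean error is small (−0.7 day for the 15th, −1.9 days for 30 June), but it can end a line before it began. With starts uniform over two years and exponential durations of mean 120, 180 and 300 days, 25%, 19% and 13% of year-only stops would precede their own start, and about 3%, 2% and 1% of day-missing stops. The current convention cannot do this.

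**Conclusion.** The point holds for durations and for impossible date sequences. Followed literally, SAP Section 7 lengthens palbociclib and line durations for records with partial dates and never shortens them. It also permits an imputed stop after death, last contact, the data cut or the next line's start when these lie in the same month or year. The averages rest on uniform calendar dates; the direction does not.

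The bias in the reported means cannot be sized from the documents. It may be a few days or less if partial dates are rare and only days are missing, and over a month if year-only stops are common. The documents support no claim about rwPFS or OS through line stop dates, and no claim that gap errors share one sign. Because the outputs serve the study's primary goal and the remedy needs no data, the change should be made.

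**What to change.** Keep the current convention in SAP Section 7 and bound it:

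- An imputed stop is the earliest of the rule's value, the day before the next line starts, the death date, the last contact date and the data cut, and never before its own line's start.
- An imputed start is no earlier than the day after the previous line's known stop.
- State the order when adjacent dates are both partial, for example set starts first, then cap stops. If both are recorded only as June, that order gives a stop of 31 May, outside the recorded month, so the SAP should say how such ties are handled.
- Report the number of imputed start and stop dates, by type, beside the duration tables, so that readers can judge the remaining bias.

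Separately, correct the Appendix 1 derivation of the gap between lines so that it starts at discontinuation, as its title and Section 8 require. Compute it as a signed difference, so that an overlap is shown as negative and not as a positive gap.

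The cost is SAP wording and a few lines of derivation code. No new data are needed.
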